## **13. Data Analysis, Evaluation and Statistical Plan**

### **13.1. Analysis Populations**

Analyses will be performed within both the intent-to-treat (ITT) population of all enrolled patients and among the subset of patients who complete the study. Patients may be missing endpoint data at one or more, or possibly all, post-screening time points, at which endpoint data will be provided by carrying forward the most recent observation. Enrollment will continue until 80 subjects complete the study. Expecting 15% dropout, the anticipated total enrollment will be approximately 94 patients.

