### **13.2. Analysis of Efficacy and Sample Size**

Using data collected at each of Study Visits 2, 3, and 4, percent change from screening at each time point will be calculated for each patient with respect to frequency of OAB symptoms, including 3-day daily averages of daytime voids, urge events, nighttime voids, and urge incontinent events. The maximum percent improvement across the four symptoms will also be calculated at each time point as a composite endpoint. Percent improvement in daily average total voids relative to an upper normal limit of 8, will also be calculated, and will be bounded below at 0% for patients not achieving improvement and bounded above at 100% for patients achieving or surpassing the upper normal limit of 8. Longitudinal analyses will be performed using repeated measures models to assess and describe trends over time with respect to these endpoints. At individual time points, the one-sample T-test will be performed at significance level  $\alpha=0.05$  within each treatment group and for the pooled study groups to assess the mean percent improvements, with 95% confidence intervals for mean percent improvements also calculated. The percent change endpoints are not likely to have approximately normal distributions, but the sample size is considered sufficient such that mean values will be approximately normally distributed, justifying the use of the T-tests. If there is concern with the distributions, then the Wilcoxon signed rank test will be used as an alternative to the one-sample T-test.

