Sample size is evaluated by the performance of the 95% confidence interval for mean percent improvement percent improvement in daily average total voids relative to an upper normal limit of 8. Log ratios of daily average event frequencies at post-screening time points relative to the daily average event frequencies at baseline, which are mathematically related to the percent changes from baseline, are more likely than percent changes to have approximately normal distributions. If such log ratios are normally distributed so that in both treatment groups the median percent improvement (toward zero) in daily average total voids is 15% and so that 25% of patients will achieve a 50% improvement, then with a total evaluable sample size of 80 patients completing the study, there is an estimated 95.6% power to conclude that the mean percent improvement in daily average total voids relative to an upper normal limit of 8 is 25% or larger using the 95% confidence interval. Within each treatment group of size  $n=40$ , there is an estimated 90.8% power to conclude that the mean percent improvement in daily average total voids relative to an upper normal limit of 8 is 20% or larger using the 95% confidence interval.

Two-sample T-tests performed at a significance level  $\alpha=0.05$  will be used to compare the treatment groups with respect to mean percent improvements in frequency of OAB symptoms, and with respect to results of OAB questionnaires. If there is concern with the non-normality of the distributions of these endpoints, then the Wilcoxon rank sum test will be used as an alternative to the two-sample T-test. Linear models will be constructed as extensions of the one-sample and two-sample T-tests to allow for assessments of mean percent improvements and group comparisons with covariate adjustments.

Frequencies of responders at individual time points and over all time points will also be calculated, where a responder for a given OAB symptom is defined as a subject achieving 50% improvement in frequency, and a responder for the composite collection of OAB symptoms is defined as a subject achieving 50% improvement in frequency for at least one symptom frequency. The treatment groups will be

compared with respect to response frequencies using chi-square or Fisher's exact tests, and exact 95% binomial confidence intervals will be calculated.

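### The pooled interval behind the 25% statement should carry a term for randomised arm and weight the two schedules equally; the gain is small but almost free

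*Combined protocol and SAP*

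**What the plan says.** Section 13.2 (Analysis of Efficacy and Sample Size) uses the one-sample T-test and its 95% interval at individual time points, "within each treatment group and for the pooled study groups to assess the mean percent improvements, with 95% confidence intervals for mean percent improvements". The sample-size paragraph of that section rests on the same interval. With 80 completers "there is an estimated 95.6% power to conclude that the mean percent improvement in daily average total voids relative to an upper normal limit" (that limit being 8 voids per day) reaches at least 25%. Within each arm of 40, the corresponding statement is 20% or larger, with power 90.8%. The planning scenario assumes that "in both treatment groups the median percent improvement (toward zero) in daily average total voids is 15"%, with the spread fixed "so that 25% of patients will achieve a 50% improvement". The endpoint is "bounded below at 0% for patients not achieving improvement and bounded above at 100% for patients achieving or surpassing the upper normal limit of 8".

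Section 13.1 (Analysis Populations) sets the stopping rule: "Enrollment will continue until 80 subjects complete the study". That is a total, not 40 per arm. The same section calls for analysis of all enrolled subjects, with the last observation carried forward, as well as of completers.

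Section 13.2 also commits to linear models that extend the one- and two-sample tests with covariate adjustment. It names no covariate.

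**The concern.** Section 4 (Objectives) lists first the comparison of one session a week with three. A pooled one-sample interval takes the opposite starting point, that all subjects come from a single population. Two things follow if the schedules do differ.

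First, the sample standard deviation absorbs the gap between the arm means. Under 1:1 randomisation that gap is a fixed feature of the design and not sampling error in the average of the two arm means, so the interval is wider than it needs to be.

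Second, an unweighted mean over completers gives each schedule the weight of its completer count. The estimate then describes whatever mix happened to finish, not the 1:1 mix that was randomised.

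At stake is the precision and the meaning of the one pooled figure on which the sample size was judged. The comparison of the two schedules is not affected.

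**Working it through.** **Inputs**

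- From Section 13.2: median ratio 0.85; 25% of subjects at a ratio of 0.50 or less; score = (B − post)/(B − 8), clipped to 0–100%; two-sided 95% T interval; n = 80 with bar 25%, n = 40 with bar 20%.
- From Section 13.1: 80 completers in total, 15% dropout, about 94 enrolled.
- Assumed: B, the screening voids per day. Section 6 gives only a floor of 10, so B was varied.

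**1. Reproduce the printed powers**

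SD of the log ratio = (ln 0.85 − ln 0.50)/0.6745 = 0.787. Simulating the clipped score with a constant B = 16.5 gives power 95.5% (n = 80, bar 25%) and 91.0% (n = 40, bar 20%), against the printed 95.6% and 90.8%. Every B tried from 15.5 to 17 comes within 2 points of both. At B = 12 the results are 99.6% and 97.6%, so the match depends on B. The printed figures are coherent for the analysis as planned.

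At this B the within-arm SD of the score is s ≈ 0.433. The pooled half-width is 1.99 × 0.433/√80 = 0.096, or about 9.6 points.

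**2. Spread counted as noise**

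With 40/40 completers and a true arm difference d, the pooled variance is s² + d²/4. The ratio of the plain SE to the within-arm SE is therefore √(1 + d²/(4s²)).

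| d (points) | Calculation, s = 0.433 | SE too large by |
|---|---|---|
| 0 | √1 | 0% |
| 14 | √(1 + 0.0049/0.1875) = 1.013 | 1.3% |
| 28 | √(1 + 0.0196/0.1875) = 1.051 | 5.1% |

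Holding s fixed understates the last row slightly, because clipping shrinks the spread in the weaker arm. At 28 points the two arm SDs are about 0.432 and 0.395 (root mean square 0.414), and √(1 + 0.0196/0.1714) = 1.056, or about 6%. The choice of B matters little here: with s = 0.480 (B = 10) or 0.411 (B = 20), held fixed, the excess is 1.1% to 1.4% at 14 points and 4.2% to 5.6% at 28 points. The direction is always conservative.

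**3. Drift in the completer set**

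Drift = (n₁/80 − 0.5) × d. At 43/37 this is 0.0375 × 14 = 0.5 point and 0.0375 × 28 = 1.05 points. If 94 subjects are allocated 47/47 and 14 drop out, 43/37 means 4 dropouts in one arm and 10 in the other. With equal dropout risk, a split at least that uneven has a chance of about 15% (hypergeometric: 14 drawn from 47 + 47). A 46/34 split needs 1 against 13, with a chance of about 0.08%.

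**4. What the arm model costs**

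The equally weighted mean has SE = (s/2)√(1/n₁ + 1/n₂). Relative to s/√80 this is 1.000 at 40/40. At 46/34 it is (√80/2) × √(1/46 + 1/34) = 1.011, about 1% larger if the arms are truly equal. Moving from 79 to 78 degrees of freedom changes power by less than 0.01 point.

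**The case against.** The strongest reply is that the effect is small and errs on the safe side. Under the plan's own assumption of equal medians in both arms, the plain interval is exact. When the arms differ it is slightly wide, so it does not inflate false claims. Drift of 0.5 to 1.0 point is minor beside a half-width of 9.6, and the analysis of all enrolled subjects keeps everyone randomised, so only a chance imbalance in allocation could shift the mean there. All of this stands, and it sets the rank of the point: a cheap improvement, not an error that threatens a conclusion.

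A second reply is that the linear models already cover the matter. They are a commitment and not an option, and that much stands. But with no covariate named they do not commit the sponsor to arm, to equal weights, or to using the adjusted interval for the 25% statement.

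A third is that the 25% bar appears only in the sample-size paragraph and no section makes it a formal success rule. That is correct, and it limits what turns on the interval.

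**Conclusion.** The point holds for the pooled interval only. That interval is exact if the arms are equal, about 1% too wide in SE at a 14-point arm difference and about 6% at 28 points. The completer mean drifts about 0.5 to 1.0 point at 43/37. These sizes rest on the planning log-normal model and an assumed 16.5 voids per day at screening.

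A reader might infer three stronger things that the documents do not support.

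- **That the 20% statements share the defect.** They are made within each arm, so they can neither ignore arm nor drift between arms.
- **That the intervals are also too narrow because up to 12 sites take part.** This depends on an intraclass correlation (ICC) that the documents do not give. At an assumed 0.05 with 12 equal sites, the design effect is 1 + (6.67 − 1) × 0.05 = 1.283, the SE is 13% too small relative to the plain one (√1.283 = 1.133 times as large when corrected), and nominal 95% coverage is about 92%. At zero there is no effect. Nor is the remedy free: inference from 12 sites on 11 degrees of freedom cuts pooled power from about 95% to 91% even with no site effect, and a simple clustered SE still covers only about 91–93% when sites are very unequal.
- **That the printed 95.6% is wrong.** It reproduces for the planned test. Lower figures describe a different method.

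**What to change.** In Section 13.2, replace the pooled one-sample T interval with a linear model of the score on randomised arm. Report the equally weighted average of the two arm means, with its SE from the within-arm variance, in both the all-enrolled and completer sets. State that this interval is the one used for the 25% statement.

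The cost is a sentence in the plan, one degree of freedom, and an SE about 1% larger if completers split as unevenly as 46/34 while the arms are equal. Equal weighting restores the randomised mix of schedules. It does not remove any selection that dropout causes within an arm.

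Leave the per-arm 20% intervals and the printed powers as they are. A random-site or site-clustered interval may be added as a sensitivity analysis, labelled as such, with a small-sample correction.

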#### **4. Objectives**

- To compare the effectiveness of 1 treatment session per week to 3 treatment sessions per week on OAB symptoms using the Test Article.
- To evaluate the overall effectiveness
- To evaluate any side effects of the Test Article.
- To evaluate the tolerability, usability, and satisfaction of the Test Article.
- To evaluate the compliance by subjects using the Test Article.

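### The 1-versus-3 sessions comparison has no main model and no stated detectable difference, and its named T-test uses the scale the plan itself expects to be less normal

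*Combined protocol and SAP*

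**What the plan says.** The first-listed objective in Section 4 is "To compare the effectiveness of 1 treatment session per week to 3 treatment sessions per week on OAB symptoms using the Test Article". Subjects are randomized 1:1 for this comparison, and Section 5.1 calls it an evaluation of dose response that will help to plan a larger study.

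Section 13.2 deals with it in three places.

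- **Test.** "Two-sample T-tests performed at a significance level" of 0.05 "will be used to compare the treatment groups with respect to mean percent improvements in frequency of OAB symptoms", and also for the questionnaires. Wilcoxon rank sum replaces the T-test if non-normality causes concern; no criterion is given.
- **Models.** Linear models extend the T-tests to allow "group comparisons with covariate adjustments". Repeated-measures models describe trends over time. No covariate is named, no between-arm contrast over time is stated, and no model is designated as the main one.
- **Sample size.** "Sample size is evaluated by the performance of the 95% confidence interval for mean percent improvement" in total voids relative to a limit of 8. The assumption is that "in both treatment groups the median percent improvement (toward zero) in daily average total voids is 15" percent, "so that 25% of patients will achieve a 50% improvement", "with a total evaluable sample size of 80 patients completing the study". Power is stated for the pooled group (95.6%) and for each arm alone (90.8%), but not for a difference between arms.

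Section 13.2 also says that percent changes are unlikely to be close to normal and that log ratios are more likely to be. It uses the log scale for sizing and percent changes for testing.

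**The concern.** The randomized question has no planned difference, power or target precision. Because both arms are given the same effect, the planned difference is zero. The named test uses the scale that the plan considers the less suitable, and the choice between T-test and Wilcoxon can be made after the data are seen, in an open-label trial (Section 6.1).

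If the response is as variable as the sizing assumes, a moderate advantage of three sessions over one would probably give a non-significant result. The plan does not say how such a result would be read. The result is meant to inform a larger study (Section 5.1), and the trial's data are to support device clearance (Section 17.1).

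**Working it through.** **Inputs.** From Section 13.2: median improvement 15% in both arms, 25% of patients reaching 50% improvement, 80 completers, α = 0.05. With 1:1 allocation this is 40 per arm, the group size Section 13.2 uses. Sidedness is not stated and is taken as two-sided. The entry minimum is an average of 10 frequency events per day (Section 6). The documents do not give the baseline distribution, so it is assumed.

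**1. The plan's own figures.** With normal log ratios, mean = ln 0.85 = −0.1625 and SD = ln(0.85/0.50)/0.6745 = 0.5306/0.6745 = 0.787. The sizing endpoint is (B − B × ratio)/(B − 8), bounded at 0 and 1, where B is baseline voids per day. Success means that the lower limit of the two-sided 95% t interval reaches the threshold. Simulated power:

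| B | n = 80, mean ≥ 25% | n = 40, mean ≥ 20% |
|---|---|---|
| 10 | 100.0% | 99.1% |
| 12 | 99.6% | 97.4% |
| 16.4 | 95.7% | 91.1% |
| 20 | 88.0% | 84.5% |

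The stated 95.6% and 90.8% are matched at B of about 16 to 17. That B is fitted, not documented, but the match supports 0.787 as the planning spread. Enrolment also reproduces: 80/0.85 = 94.1.

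**2. Detectable difference between arms, in SD units.** (1.960 + 0.842) × √(2/40) = 0.627 SD; the exact t calculation gives 0.634 SD.

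**3. Log scale.** 0.634 × 0.787 = 0.499, and 1 − exp(−0.499) = 39% fewer voids in one arm. The other arm improves by a median of 15%, so this one would have to improve by 1 − 0.85 × 0.607 = 48%. The whole assumed effect on this scale is 0.1625. The 95% CI for the ratio of voids has log half-width 1.99 × 0.787 × √(2/40) = 0.350, a factor of about 1.4 either way.

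**4. Bounded 0–100% endpoint.** The SD is 0.43 (B = 16.4) to 0.48 (B = 10). The detectable difference is 0.634 × 0.43 = 27 points to 0.634 × 0.48 = 30 points, against an assumed mean of 42.5% to 52.7%. The 0% floor inflates that mean: with no median change it would still be about 35% (B = 16.4) or 41% (B = 12). Power to separate an arm with the full assumed effect from one with none is only 12% to 13%.

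**5. Power by method.** Simulation on total voids, 40 per arm, subjects selected at 10 or more per day. Ranges cover separate runs with assumed baselines.

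| Log-SD | True difference | T-test, percent change or bounded | Log-scale model |
|---|---|---|---|
| 0.787 | 22% fewer | 22–23% | 28% |
| 0.787 | 39% fewer | 64–68% | 77–79% |
| 0.3 (assumed) | 15% fewer | 65% percent change, 59% bounded | 66% |

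Normal-approximation check of the first row: −ln 0.78 = 0.248; 0.248/0.787 = 0.316 SD; 0.316/√(2/40) = 1.41; Φ(1.41 − 1.96) = 29%. Type I error was held. Over assumed spreads of 0.2 to 0.3 the gain was about 1 to 7 points.

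**6. Source of the gain.** For 22% fewer voids at log-SD 0.787, an unadjusted T-test on the log ratio had 28.3% power and the model adjusted for log screening voids 28.1%. With 10% diary noise the two differed by 0.1 point (27.8% and 27.7%). Wilcoxon on percent change had 26–27%.

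**The case against.** **Adjustment is planned.** A reader might infer that the comparison is unadjusted and that available precision is thrown away. Section 13.2 does not support that: it commits to covariate-adjusted linear models for group comparisons and to repeated-measures models. What remains is that the covariates are unnamed and no model is designated as main.

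**Baseline adjustment is not the remedy.** This stands. Percent change and log ratio already use baseline, so nearly all the gain comes from the log scale. Adding log screening voids brings at most about a point, and only when the spread is small and the diary noisy.

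**Wilcoxon already recovers much of the gain** at the plan's spread. This also stands. However, Wilcoxon is a fallback without a criterion, and the plan attaches no effect estimate to it.

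**Low power depends on the spread.** At log-SD 0.2 to 0.3, the T-test for 22% fewer voids has 89–100% power on percent change and 84–100% on the bounded endpoint. That is correct, but 0.787 is the spread implied by the plan's own sizing.

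**Estimation is a defensible aim** for a study that prepares a larger one. It is, but Section 13.2 gives no target precision for the difference.

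**Conclusion.** The concern holds as a gap in specification with a moderate and measurable cost. The plan should be changed, but this does not invalidate the trial. The first-listed objective has no stated detectable difference and no main model, and the named T-test is less powerful than a log-scale analysis: by about 6 points for 22% fewer voids and about 12 points for 39% fewer at log-SD 0.787, and by about 1 to 7 points at 0.2 to 0.3.

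Two stronger readings should be avoided. A reader might infer that the detectable difference exceeds the whole assumed effect on every scale. It does on the log scale (0.50 against 0.16), but not on the bounded sizing endpoint (27 to 30 points against a mean of about 42% to 53%); those points must not be set beside the 15% median, which is defined toward zero. A reader might also infer that the plan intends to claim that one session is as good as three. It makes no equivalence or non-inferiority claim; it only leaves the reading of a null result open.

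The figures rest on two-sided α, 40 completers per arm, normal log ratios and assumed baselines. They concern total voids, the only variable for which Section 13.2 gives planning values.

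**What to change.** In Section 13.2:

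1. Name one main 3-versus-1 comparison: a linear or repeated-measures model of log daily average total voids, with arm and log screening voids, at one named time point.
2. If that point is Week 12, add Visit 5. Section 13.2 lists only Visits 2, 3 and 4, and Week 12 is Visit 5 (Section 7.11).
3. Report the adjusted ratio with its 95% CI, also expressed as a percent difference.
4. Keep the percent-change T-test and Wilcoxon as sensitivity analyses, and delete the data-dependent switch for the main comparison.
5. State that 40 per arm detects 0.63 SD at 80% power, about 39% fewer voids under the planning assumptions, and that p > 0.05 will not be read as equivalence.

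**Cost.** Wording only; no further patients or data. The main effect becomes a ratio of geometric means instead of a difference in mean percent improvement, and the stated detectable difference is unflattering. Power for 22% fewer voids stays near 28% at the plan's spread, so the change improves the analysis without making the comparison well powered.

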### **13.3. Analyses of Tolerability, Usability, and Satisfaction**

Subject responses to questions regarding tolerability, usability, and satisfaction, will be tabulated.

### **13.4. Analyses of Safety**

All adverse events will be collected as they occur and tabulated.

## **14. Withdrawal of Subjects from Study**

Subjects may be discontinued from the study for non-treatment-related reasons only when no other option is possible. Reasons for discontinuation include, but are not necessarily limited to:

1. Voluntary withdrawal from the study by the subject.
2. Subject is unwilling or unable to cooperate with study requirements.
3. Subject has an adverse event such that they can no longer continue with stimulation.

The reason for discontinuation will be recorded on the appropriate subject Withdrawal form. Discontinued subjects may not be replaced in the study.

Prior to discontinuing a subject, every effort should be made to contact the subject in an effort either to get the subject back into compliance with the protocol, or to obtain as much follow-up data as possible.

## **15. Modification of Protocol**

Any amendments to this protocol must be prepared by the Study Monitor and approved by Aviation Medical, the Investigator, and the central or local authority (IRB/IEC) before implementation.

## **16. Discontinuation of Study**

Aviation Medical reserves the right to discontinue any study for administrative reasons at any time, such as but not limited to, a decision to discontinue further clinical investigations with the Test Article, improper conduct of the Study by the Investigator, inability to obtain the number of subjects required by the protocol, etc. Reimbursements for reasonable expenses will be made if such action is necessary.

